## 2) Objectives

The overall objective of this study is to test the efficacy of virtual family-centered rounds (FCR) compared to standard rounds for NICU patients and to conduct an intervention evaluation of the virtual FCR intervention.

**Aim 1: Evaluate the impact of virtual FCR on parental activation and wellbeing.** The primary outcome will be FCR parent attendance proportion (number of round encounters with a parent present – either virtually or in person – divided by total number of round encounters). Increased parent FCR attendance would increase the delivery of best practice. We will also compare parent experience (Child HCAHPS) and parent activation (P-PAM) at discharge and parent distress and quality of life at 0, 30, 60, and 90 days from discharge between assigned trial arms. Parent wellbeing promotes neonatal wellbeing.

- *Hypothesis1a: The virtual FCR (intervention) group will have a higher parent FCR attendance proportion compared to the standard FCR (control) group.*
- *Hypotheses1b: Parents of virtual FCR neonates will report (a) better experience, (b) higher activation, (c) less distress, and (d) better quality of life compared to parents of standard-of-care neonates.*

**Aim 2: Evaluate the impact of virtual FCR on neonatal outcomes.** We will compare breast milk feeding at discharge and 90 days from discharge, growth failure, medical errors, and NICU length of stay between assigned trial arms.

- *Hypotheses2: Virtual FCR neonates will have (a) greater breast milk feeding, (b) reduced growth failure, (c) fewer errors, and (d) shortened length of stay compared to standard-of-care neonates.*

**Aim 3: Conduct a mixed methods evaluation of the virtual FCR intervention.** We will measure all five RE-AIM dimensions using quantitative (chart review, surveys) and qualitative (observations, interviews) methods. Observations will be of NICU FCR; interviews will be with intervention arm parents and NICU providers. We will use a convergent design and merge data in the analysis and reporting phases.

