#### **4) Inclusion and Exclusion Criteria**

This study is a randomized trial to compare virtual family-centered rounds (**FCR**) to standard FCR for neonatal intensive care unit (**NICU**) patients. We will simultaneously conduct an intervention evaluation of this virtual FCR intervention. The unit of randomization is at the subject level (the neonate). The site is the UC Davis NICU. To gather necessary data on efficacy outcomes and on the 5 dimensions for the intervention evaluation (Reach, Effectiveness, Adoption, Implementation, Maintenance), survey data will be collected from the subjects’ parent or guardian (referred to as “parent” hereafter), electronic health record (EHR) data will be collected from UC Davis, and daily weekday FCR observations will be performed. To gather necessary data for the intervention evaluation, qualitative interviews will be performed.

- INCLUSION: (NEONATES) Neonates aged <365 days admitted to UC Davis neonatal intensive care unit (NICU) during the study period who have one or more parent or guardian that self-reports their preferred language to be English. This parent must also be non-incarcerated and aged  $\geq 18$  years.
- EXCLUSION: (NEONATES) Age > or = 365 days. Neonates with visitation or information restrictions placed by child protective services. Neonates with more than one admission during the trial period will be included only on their first admission.
- INCLUSION: (QUALITATIVE INTERVIEWS) Parents/guardians of the eligible patients (described above) and NICU clinicians (e.g., nurses, physicians). Age 18 years and older.
- EXCLUSION: (QUALITATIVE INTERVIEWS) Age less than 18 years. Non-English speaking.
- INCLUSION: (SURVEY) Parents/guardians of the eligible patients (described above). Age 18 years and older.

**PROTOCOL TITLE: Virtual Family-Centered Rounds in the Neonatal Intensive Care Unit:  
A Randomized Clinical Trial**

- EXCLUSION: (SURVEY) Age less than 18 years. Non-English speaking.

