**5) Study Timelines**

We anticipate this trial will begin ~2/1/2023. We will begin enrolling subjects at trial onset. We will enroll subjects (neonates) and assign to either the intervention or control arm for 12 months. Each subject (neonate) will be included for the duration of their hospitalization.

We will follow this 12-month period with 1 month of rounding observations for data collection. We will also continue to collect surveys at 0, 30, 60, and 90 days from discharge. Therefore, survey data collection will continue until 16 months from the trial onset.

Regarding qualitative interviews for the intervention evaluation (Aim 3), those will continue for 18 months from the trial onset.

The estimated date to complete this study is therefore ~8/1/2024.

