**DATA COLLECTION:** Data collection will include daily weekday virtual FCR observations; parent surveys; and review of the EHR, incident reports, and helpdesk technical issues log. Outcomes (for Aims 1-3) will include the following: FCR parent attendance proportion (captured using weekday rounding observations), length of stay (captured using EHR data), breast milk feeding initiation and breast milk feeding at discharge (captured using EHR data) and at 90 days after discharge (captures via parent via parent/guardian survey), growth failure and growth velocity (captured using EHR data), time to first social work contact (captured using EHR data), temperature instability (captured from an existy NICU quality dataset), feeding difficulty (captured from an existy NICU quality dataset), central line-associated bloodstream infection (captured from an existy NICU quality dataset), central line days (captured from an existy NICU quality dataset), antibiotics days (captured from an existy NICU quality dataset), medical errors (captured using data from EHR, incident reporting system, and solicited reports), 30-day revisit and readmission (captured via EHR and survey) parent experience and family-centered care (captured via parent/guardian survey at discharge), parent activation (captured via parent/guardian survey at discharge), parent distress: depression and anxiety (captured via parent/guardian survey at 0, 30, 60, 90 days from discharge), parent sleep (captured via parent/guardian survey at 0, 30, 60, 90 days from discharge), and parent quality of life (captured via parent/guardian survey at 0, 30, 60, 90 days from discharge).

RE-AIM (Aim 3) implementation evaluation data collection will include the

**PROTOCOL TITLE: Virtual Family-Centered Rounds in the Neonatal Intensive Care Unit:  
A Randomized Clinical Trial**

following: subscribed vs. not subscribed parents among intervention-arm parents, heterogeneity of intervention effects (interactions between neonate/parent characteristics and the intervention effect), virtual FCR attempts with technical issues (sounds, video, other), trial-related 24/7 helpdesk line calls, ExtendedCare wait time when parent(s) join, ExtendedCare connection time, device model (e.g., iPhone, Android, etc.) that parent uses to connect to the ExtendedCare visit, interruptions requiring a break in rounds due to a delivery or new admission, and virtual FCR use with NICU parents post-trial (maintenance).

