## 18) Provisions to Protect the Privacy Interests of Subjects

All information will be kept in secure REDCap or Excel databases and the only link between the patient and the REDCap will be a Study ID. We will use a "Participant Log" excel file to store data that links the Study ID with the subject. This log will include the following information: Study ID, patient name, MRN, CSN, intervention vs. control arm, admit date, enrolled date, parent identify (e.g., "mom"), parent cell/email preferred contact, subscription status, and disposition. This "Participant Log" will be stored on the secure UC Davis server.

Families will be free to use the intervention if/when it works for them. Families randomized to the intervention can opt out of using it entirely, with no penalty to them or their child. Families are free to answer (or not answer) the surveys the week of discharge and at 30, 60, and 90 days after discharge, with no penalty to them or their child.

Only members of the research team will have access to the data.

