## STATISTICAL ANALYSIS PLAN

### Statistical methods for primary and secondary outcomes

Our primary analysis strategy will analyze all available data from participating family units and their members, with groups defined according to the randomized assignment (intervention versus control) for that family unit. We will use graphical and analytical descriptive statistics to summarize infant, parent, and family unit characteristics. We will use methods for clustered survey data to adjust confidence intervals for family units with multiple parental respondents. We will not use cluster-adjusted confidence intervals for family units with multiple infants unless the mean number of infants per family unit unexpectedly exceeds 1.10.

We will use generalized linear models to estimate intervention effect sizes and confidence intervals and to test hypotheses for outcomes. Independent variables will include a binary indicator for intervention assignment along with a parsimonious set of subject characteristics as covariates (parent age, race, ethnicity, gender, education, transportation security, marital status, other children dependents, digital literacy score). We will specify the generalized linear mixed models as linear, logistic, or Poisson regressions, according to the outcome type. Random effects will be specified to accommodate the multilevel structure of the data and the nesting of longitudinal measurements, when applicable, within parents and the nesting of parents and infants within family units.

To account for increased exposure among subjects with longer neonatal intensive care unit (NICU) stays when analyzing the primary outcome, we will use Poisson regression to compare rates for the family-centered rounds (FCR) parent attendance outcome between intervention vs. control group subjects, using the numerator for this outcome as the dependent variable and using the logarithm of the denominator as an offset term. We will also use Poisson

regression for analyzing the error rate outcomes, with the offset being the logarithm of the number of days in the NICU. The exponentiation of the Poisson regression coefficient for the treatment indicator will thus represent an adjusted between-arm rate ratio for FCR parent attendance.

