For parent experience and family-centered care, we will use the top-box scoring method and assess intervention effects on the individual items as well as on the summary scores. For parent health-related quality of life (HRQOL), we will similarly assess the intervention effects on the PedsQL™ Family Impact Module 36 items, eight subscales, and summary scores (overall total score, Parent HRQOL Summary score, and Family Functioning Summary score). To accommodate the longitudinal data collection for the HRQOL outcomes, we will use generalized linear mixed models that include main effects for time, study arm, and the interaction, to estimate timepoint-specific intervention effects. We will also evaluate the effect of the intervention on the remaining outcomes.

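### Breast milk feeding initiation has no time origin or at-risk definition, so starts before assignment can count as outcomes, and feeding status at assignment is not used for Hypothesis 2a (minor)

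*Combined protocol and SAP*

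**What the plan says.** Protocol section 7 (Data Collection) lists among the outcomes for Aims 1 to 3 "breast milk feeding initiation and breast milk feeding at discharge (captured using EHR data". Initiation is thus a separate item from feeding at discharge. It is not defined further.

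Aim 2 in section 2 is narrower: "We will compare breast milk feeding at discharge and 90 days from discharge, growth failure". Initiation is named neither there nor in the SAP. It enters the analysis through general statements. Section 8 applies generalized linear models to the study outcomes. The SAP adds "We will also evaluate the effect of the intervention on the remaining outcomes", and on the population it says "Our primary analysis strategy will analyze all available data from participating family units and their members", grouped as randomised.

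On timing, section 4 admits "Neonates aged <365 days admitted to UC Davis neonatal intensive care unit (NICU) during the study period" and sets no feeding-status criterion. Section 5 says "Each subject (neonate) will be included for the duration of their hospitalization". The participant log in section 18 holds "intervention vs. control arm, admit date, enrolled date" as separate fields. No section limits the time from birth or admission to assignment.

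The SAP names nine covariates, all describing the parent or family (for example education, marital status and digital literacy). Section 8 of the protocol speaks of clinical as well as demographic covariates but names none.

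For medical errors, the SAP specifies a Poisson model "with the offset being the logarithm of the number of days in the NICU".

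**The concern.** Initiation is an early-life event. For an infant admitted weeks or months after birth it may be settled before admission, and for others it may occur between admission and assignment. An event that precedes assignment cannot be caused or prevented by virtual rounds. Infants who had already started carry no information on the effect, yet an analysis of all available infants would include them. The estimated difference is then smaller than the effect in infants who could respond, and power is lower. With the definition left open, the counting rule could also be chosen after the data are seen.

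The same EHR information, read at the enrolled date, is the baseline version of the feeding outcomes in Hypothesis 2a. Leaving it out of those models gives up precision that should cost little to obtain.

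**Working it through.** **1. The plan's own figure.** Inputs from section 8: log length of stay SD 1.0, 25% reduction in geometric mean, two-sided alpha 5%, power 80%, 2:1 allocation, 4% attrition.

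- Control n = (1 + 1/2) × (1.960 + 0.842)² × 1.0² / (ln 0.75)² = 1.5 × 7.849 / 0.0828 = 142.3, so 143.
- With 286 in the intervention arm the total is 429, and 429 / 0.96 = 446.9, so 447.

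The stated size reproduces. It rests on length of stay and is untouched by this point. No rate, target difference or power is given for initiation.

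**2. Dilution.** Let s be the share started before assignment, and p0 and p1 the initiation proportions in the rest (control, intervention). Counting everyone, each arm's proportion is s + (1 − s)p, so the difference is (1 − s)(p1 − p0). This holds for any s.

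**3. Power.** The documents give neither s nor p. Assume p0 = 40%, p1 = 60%, and 143 vs 286 analysed. Power = Φ(d/SE − 1.96), with SE² = P0(1 − P0)/n0 + P1(1 − P1)/n1. For s = 50%:

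- All infants: 70% vs 80%; SE = √(0.21/143 + 0.16/286) = 0.0450; 0.10/0.0450 − 1.96 = 0.26; power 60%.
- Not yet started: 40% vs 60% in 71.5 vs 143; SE = √(0.24/71.5 + 0.24/143) = 0.0710; 0.20/0.0710 − 1.96 = 0.86; power 80%.

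| Share started (assumed) | Difference, all infants | Power, all infants | Power, not yet started |
|---|---|---|---|
| 50% | 10 points | 60% | 80% |
| 70% | 6 points | 36% | 59% |
| 85% | 3 points | 19% | 34% |

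A pooled variance under the null moves these by at most about 4 points and leaves the ordering. A second assumed pair, 50% vs 65% (pooled variance), gives 45% against 56% at s = 50% and 24% against 32% at s = 75%. In each case the restricted analysis has more power with fewer infants, but it does not recover what s = 0 would give.

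**4. Feeding status as a covariate.** A binary baseline with prevalence q, and outcome proportions a (started) and b (not started), explains R² = q(1 − q)(a − b)² / [m(1 − m)] of the variance, where m = qa + (1 − q)b. All inputs are assumed.

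- q = 0.6, a = 0.80, b = 0.15: m = 0.54, R² = 0.24 × 0.4225 / 0.2484 = 41%, and 1/(1 − R²) = 1.69.
- q = 0.8, a = 0.70, b = 0.35: m = 0.63, R² = 0.16 × 0.1225 / 0.2331 = 8%, and 1/(1 − R²) = 1.09.

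On a linear scale this equals roughly 9% to 69% more infants. The SAP would use logistic regression for a binary outcome, so this indicates possible size only.

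**5. Error model.** With log stay 3.0 ± 1.0 and a lognormal shape, mean stay is exp(3.5) = 33.1 days. An assumed lag of 1 to 5 days from admission to assignment puts a fraction f of about 3% to 15% of NICU days before assignment. With equal error rates in both arms during the lag, a true rate ratio of 0.75 becomes f + 0.75(1 − f), that is 0.76 to 0.79.

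**The case against.** The strongest reply is that little here is established by the documents. A reader might infer that many infants will have started before assignment. The upper age limit gives no age distribution, however, and two date fields in a log show that both dates are kept, not that they differ materially. A reader might also infer that earlier starts will certainly be counted. Initiation is undefined, and the section 5 statement on inclusion can be read as running from enrolment. Nor do the documents show how strongly early feeding predicts later feeding. All of this stands: what can be supported is that the plan permits such counting, not that it requires it.

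A further tempting reading is that the comparison is biased, or that chance imbalance inflates false positives. It does not hold. Randomisation balances earlier starts in expectation, and chance imbalance is already covered by the 5% level.

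The size of the dilution also depends on the scale. Under the logistic model and the 40% vs 60% assumption, the odds ratio falls from 2.25 to 1.71, 1.61 and 1.55 at 50%, 70% and 85% started. It tends to 1.5, not 1. The power loss remains.

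Two more points stand. Initiation is a minor outcome, absent from Aim 2 and the SAP. Also, section 4 takes EHR data from UC Davis, so feeding elsewhere before admission may be missing.

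Section 8's allowance for clinical covariates does not answer the covariate point, because the SAP's list contains none.

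**Conclusion.** The concern holds as a minor gap in definition and adjustment. Starts before assignment can be counted as initiation outcomes. They dilute the risk difference by exactly the share already started and lower power, without biasing the comparison between arms. The share is unknown. The 60% to 19% against 80% to 34% figures rest on the assumed range of 50% to 85% and on an assumed 40% vs 60% effect.

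Feeding status at assignment is a plausible, unused predictor of the Hypothesis 2a outcomes. Since those outcomes carry a stated hypothesis, this is the more useful part of the point.

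The error window is a small refinement, because section 8 already makes medical errors exploratory. Nothing here supports doubting the primary outcome or the 447.

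**What to change.** 1. In the SAP, add breast milk feeding status at the enrolled date, taken from the EHR, as a covariate in the discharge and 90-day breast milk models. Give unknown status its own category, since feeding elsewhere before admission may be incompletely recorded.
2. In section 7 and the SAP, define initiation as the first breast milk feed after the enrolled date, analysed in infants with none recorded before it. Alternatively, report initiation as a baseline characteristic and drop it as an outcome. State that the enrolled date is the date of assignment, if that is so.
3. Optionally, count medical errors and NICU days from the enrolled date.

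The cost is wording plus one further EHR extraction against a date already logged. The subset in item 2 is fixed before assignment, so the randomised comparison is preserved within it. The downsides are fewer infants in the initiation analysis and some misclassification of infants fed elsewhere. At 85% already started, power would still be only about 34% under the assumptions above, which favours the baseline option if the share proves high. Choose between the options before looking at outcomes by arm.

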**8) Data and/or Specimen Management and Confidentiality**

I understand that if this study involves the use of the UC Davis Health Electronic Health Record (EMR/EPIC) also contains the clinical data for Marshall Medical Center (MMC). I understand that MMC patient data cannot be accessed for research purposes and that I must take the necessary steps to ensure that MMC data is not accessed, used, or disclosed for UC Davis Health research purposes.

I understand that if this study involves use of UC Davis students' educational records (including records in the PI's own possession such as course exams/assignments), I must consult with the Registrar's office to see if all requirements of the Family Educational Rights and Privacy Act (FERPA) are satisfied.

**DATA ANALYSIS:** We will analyze subject data according to their assigned group (intervention vs. control). We will use descriptive statistics to summarize subject-level characteristics. We will compare neonatal and parental characteristics between study arms using Pearson's Chi-square test for categorical variables, t-test for normally distributed continuous variables, and nonparametric equality-of-medians test for non-normally distributed continuous variables. Generalized linear models will be used to estimate effect sizes and to test hypotheses for study outcomes, using a binary indicator for intervention assignment as the independent variable of interest and including a parsimonious set of demographic and clinical characteristics as covariates. We will analyze all available data and anticipate high data completion rates, based on our pilot trial. We will conduct sensitivity analyses using multiple imputation approaches for missing data to complement the primary analysis.

**SAMPLE SIZE:** We specified effect sizes of interest for all the trial outcomes and determined the necessary sample size to satisfy each. The sample size estimation that satisfies length of stay requirements also satisfies requirements for all other outcomes of interest, except for medical errors (which are rare and

**PROTOCOL TITLE: Virtual Family-Centered Rounds in the Neonatal Intensive Care Unit:  
A Randomized Clinical Trial**

thus this outcome will be considered exploratory. Outcome distributional assumptions were based on data from our pilot trial or other relevant literature. Pilot trial baseline mean log transformed length of stay +/- standard deviation (SD) was 3.0 +/- 1.0 days. Minimally clinically important differences (MCID) were based on the literature when available or via consensus opinion elicited from NICU clinicians we consulted. For the length of stay outcome, experts specified that a 25% reduction in geometric mean length of stay was of interest. A randomized sample of 447 neonates (298 intervention, 149 control) subject to 4% attrition in each arm yields a sufficient sample size (429 neonates) to provide 80% power (under two-sided testing, alpha=5%) to detect this MCID. This estimated attrition is based on 4 of 110 randomized subjects in the pilot trial being excluded from final analysis (e.g., child protective visitation restrictions placed after randomization). Parent-reported outcomes assume a survey response rate of 75% (thus n=321 parents). Note: Regarding sample size for the interviews, we anticipate interviewing ~15 parents, ~10 nurses, and ~10 physicians. Consistent with standard qualitative methods, we will continue to sample interview participants until we reach thematic saturation, thus we cannot specify a priori the exact number of interviewees.

All virtual FCR encounters will occur using an application platform that is approved by Information Technology at UC Davis Health System as meeting HIPAA and HITECH data security requirements. The only telehealth communication that will occur will be through the HIPAA-compliant application. No telehealth encounter will be recorded or stored in any way.

Participants will decide to what extent they want to participate in the interviews and surveys. There will be no personal or intrusive questions. In all steps of this pilot study, the risk of loss of confidentiality is very low given the measures described above to protect PHI.

Only trained UC Davis professionals will work directly with interview and survey participants. All verbal communication with interview participants will occur in private locations to protect the confidentiality of the material being discussed. Review of the interview recordings will take place in UC Davis private offices. Digital audio recordings will be stored using number identification that will be kept on a password-protected computer. The risk of loss of confidentiality is extremely low and is minimized by not including identifiable information in the fieldnotes as well as de-identifying the transcription data. Notes and transcriptions will be maintained in a locked cabinet in a locked UC Davis private office.

Only study personnel will have access to the study materials. The knowledge gained from this study will be disseminated in such forms as manuscripts and conference presentations; this disseminated information will contain no identifying information.

The possibility of any adverse effects on participants as result of the study intervention is minimal given the intervention (virtual FCR in the NICU) is a method of communication that has been demonstrated in prior research (a pilot trial) to improve care quality without causing harm. The difference for this present trial is that it is powered for hypothesis testing and includes additional outcome measures.

A Data Safety Monitoring Plan with an Independent Monitoring Committee will be used for this study to provide additional protection. The Independent Monitoring Committee will meet to independently review outcomes on a quarterly basis, and as needed based on any reported complications. Safety information will be collected by reviewing charts. The safety monitoring will begin when the

**PROTOCOL TITLE: Virtual Family-Centered Rounds in the Neonatal Intensive Care Unit:  
A Randomized Clinical Trial**

trial enrollment begins. The Independent Monitoring Committee will complete quarterly reports detailing the study progress, any adverse events, and any protocol deviations. The details are as follows:

- **Definition:** An adverse event is any untoward medical occurrence in a subject during participation in the study. An adverse finding can include a sign, symptom, abnormal assessment, abnormal occurrence, or any combination of these. A serious adverse event is any adverse event that results in one or more of the following outcomes: death, a life-threatening event, inpatient hospitalization or prolongation of existing hospitalization, a persistent or significant disability or incapacity, or an important medical event based upon appropriate medical judgment.
- **Classification:** Adverse events will be labeled according to severity, which is based on their impact on the neonate. An adverse event will be termed “mild” if it does not have a major impact on the neonate, “moderate” if it causes the neonate some minor inconvenience, and “severe” if it causes a substantial disruption to the neonate’s well-being.
- **Attribution Scale:** Adverse events will be categorized according to the likelihood that they are related to the study intervention. Specifically, they will be labeled definitely unrelated, definitely related, probably related, or possibly related to the study intervention.
- **Adverse Event Reporting:** Adverse events will be collected by the PI and forwarded immediately to the Independent Monitoring Committee. Events determined to be unanticipated, serious, and possibly related to the study intervention will be reported to the appropriate monitoring agencies, including the UC Davis IRB and the funding agency, within 10 days. Adverse events that are determined to be unrelated problems will be reported per IRB policy at the time of continuing review.

To conduct the intervention evalution that includes the RE-AIM dimensions, all eligible subjects will be included in the data collection process. Their data will be kept in secure REDCap databases containing only their study ID, and the link to their study ID and MRN will be kept in the “Participant Log” that is stored on a secure Excel database stored on the secure UC Davis servers.

This study is evaluating a systems-level intervention; a system-level intervention means that we are doing an intervention on how we deliver healthcare. In other words, our intervention is a test of change to the healthcare system. In this case, the system is how we deliver family-centered rounds. The study team will not be able to determine the feasibility and implementation of the pilot project without collecting the implementation data on all patients. It is important that we collect data on all eligible subjects, because we want to ensure that we include gathering data from underserved populations in order to learn how to better provide them with clinical services that meet/address their unique needs. This aspect is particularly relevant for telehealth interventions, whereby the ditigal divide is potentially designing/deliverying telehealth services that do not serve diverse populations. It is therefore important to have all of our diverse groups represented in our data in order to conduct our comprehensive intervention evaluation (Aim 3). We recognize the limitation that our survey-based outcomes (for Aims 1 and 2) will only gather data from those who complete the survey, and thus the conclusions from survey-based data will only be generalizable to similar populations as those represented in those surveys. However, our other outcomes (that rely on FCR observations and review of the EHR, incident reports, and

**PROTOCOL TITLE: Virtual Family-Centered Rounds in the Neonatal Intensive Care Unit:  
A Randomized Clinical Trial**

helpdesk technical issues log) will include all our subjects – and thus represent diverse groups.

Since this is a systems-level intervention, only collecting data on consented patients will provide Aim 3 (intervention evaluation) results that are biased and therefore not useful. We cannot understand how to refine and deliver our telehealth intervention (and thus improve this clinical service line) without having data on all eligible patients. Although we will need to collect data on every patient, the family members in the intervention group can choose if and how much to use the intervention (they can decide to never provide their cell phone number and to never use telehealth for FCR).

We will be using StudyPages, a secure web-based application developed by the UCD CTSC to maintain communication with study participants. All study personnel involved in this proposed project have received Human Subjects Protection and HIPAA education.

